15.5 Analysis of Exploratory Endpoints

The proportion of subjects discontinuing study before versus after randomization and before the end of assigned treatment duration will be tabulated by reason for discontinuation and by treatment duration arm, if randomized. Reason for discontinuations will be summarized. The screen failure reasons will be also summarized for all screening attempts. Characteristics of the un-randomized subjects by reason (e.g., lost to follow-up, missing FEV₁ or CRISS at Visit 2, patient withdrawal) will be summarized using descriptive characteristics. Similarly, the randomized but lost to follow-up subjects (no Visit 3) will be described. Comparison of these two groups with the randomized completed subjects will be performed for baseline characteristics, treatments and outcomes utilizing both the study data and the CFFNPR.

There will be descriptive summaries of adherence to antibiotic selection protocol and adherence to randomization scheme by response group (ERR and NERR), and treatment duration arm (ERR-10, ERR-14, NERR-14, and NERR-21).

Descriptive comparisons of the two cohorts treated for 14 days (ERR-14 and NERR-14) will be performed to characterize associations between early assessments of clinical response (at Visit 2) and after completion of treatment for a PEx (Visit 3).

Clinical lab CRP at each of the study visits and change in CRP from Baseline (Visit 1) will be summarized by response group (ERR and NERR) and by treatment duration arm (ERR-10, ERR-14, NERR-14, and NERR-21). Associations with CRP and change in CRP with clinical outcomes will be examined.

For all randomization arms (ERR-10, ERR-14, NERR-14, and NERR-21), quality of life and medical cost metrics will be collected for a comprehensive health economic analysis by [name] ScD, Professor and Chair, Dept. of Health Services, School of Public Health, University of Washington, Seattle according to the most recent guidance from the International Society for

Pharmacoeconomics and Outcomes Research Good Research Practices for Cost-Effectiveness Analysis Alongside Clinical Trials Task Force.

For all treatment duration arms (ERR-10, ERR-14, NERR-14, and NERR-21), the expectorated sputum will undergo analysis to describe and compare the respiratory microbiome by [name], Professor of Pediatrics and Director of Pediatric Infectious Diseases, University of Michigan, Ann Arbor.

15.6 Interim Analysis

A pre-defined monitoring plan for feasibility, variance estimation, sample size adaptation, and study stopping rules will be formalized in conjunction with the DMC and will be in place prior to initiating the study. Feasibility will be closely monitored for the first 100 enrolled patients to ensure adherence to protocol, return for randomization, and adherence to randomized treatment duration arm.

Each treatment group (ERR and NERR) will have separate monitoring criteria and a decision to stop one may not be conditional on the other.

15.7 Sample Size

ERR Group:

A non-inferiority design to show that the change in FEV₁ between Visit 1 and Visit 3 in the ERR subjects who received 10 days of treatment (ERR-10) is no more than 3.5 % predicted less than ERR subjects who received 14 days treatment (ERR-14) requires 310 subjects (155 per arm) who complete the study. STOP pilot data indicate a mean change (SD) in FEV₁ between baseline and Day 28 in patients with an early response to be 12.5 % predicted, 95% CI [9.5, 15.6]. Assuming two-sided alpha =0.05, standard deviation =9.0% predicted and the true difference between two groups is zero, the ERR study has 93% power to detect a 3.5 % non-inferiority margin which preserves 72% of the treatment effect or 63% of the lower bound of treatment effect observed in the STOP pilot.

NERR Group:

A superiority design to show that the change in FEV₁ between Visit 1 and Visit 3 in NERR subjects who received 21 days treatment (NERR-21) is at least 2.5 % predicted greater than NERR subjects who received 14 days treatment (NERR-14) requires 570 subjects (285 per arm) who complete the study. STOP pilot data indicate a mean change (SD) in FEV₁ between baseline and Day 28 in patients without an early response to be 4.0 % predicted, 95% CI [1.9, 6.1]. Assuming two-sided alpha =0.05 and standard deviation =9.0% predicted, the NERR study has 91% power to detect a 2.5% or greater increase in FEV₁ among those treated with 21 days compared to 14 day IV antibiotic. A 2.5% improvement was chosen to represent a minimal clinically important difference in lung function to justify the additional burden and potential toxicity of 21 days of treatment versus 14. It is important to note that statistical significance can be shown at the end of the superiority NERR study with a smaller treatment effect than 2.5%.

Observed treatment effect (mean difference in absolute FEV₁ change) and the 95% CI will provide primary inference and evidence of non-inferiority, superiority, or lack thereof in both the ERR and NERR groups. Motivated to ensure conclusive results, this study was designed to provide sufficiently narrow 95% CIs at the end of the trial (ERR 95% CI half-width=2%;

NERR 95% CI half-width=1.5% when both SD=9%).

Because this trial will enroll a slightly different patient population (including home IV, excluding patients who receive <7 days of IV antibiotics), a blinded, interim assessment of change in FEV₁ % predicted and variance (pooled) will be performed and expected sample size may be adjusted for either the ERR or NERR groups.

Based on STOP pilot data, we anticipate 1:2 allocation of subjects into the ERR and NERR groups. To meet the enrollment goal of a minimum of 310 completed ERR subjects and a minimum of 570 completed NERR subjects, we will screen approximately 1330 subjects. Of these, we expect approximately 1236 subjects will be enrolled and randomized (assuming a conservative 7% drop-out rate between Visit 1 and Visit 2) and a minimum of 310 completed ERR subjects and a minimum of 570 completed NERR subjects (assuming an approximate 4% drop-out rate between Visit 2 and Visit 3).

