Visit 1 and Visit 3 in the ERR subjects who received 10 days of treatment (ERR-10) is no more than 3.5% predicted less than ERR subjects who received 14 days treatment (ERR-14) requires 310 subjects (155 per arm) who complete the study. STOP pilot data indicate a mean change (SD) in FEV₁ between Baseline and Day 28 in patients with an early response to be 12.5 % predicted, 95% CI [9.5, 15.6]. Assuming two-sided alpha =0.05, standard deviation =9.0% predicted and the true difference between two groups is zero, the ERR study has 93% power to detect a 3.5 % non-inferiority margin which preserves 72% of the treatment effect or 63% of the lower bound of treatment effect observed in the STOP pilot.

NERR Group:

A superiority design to show that the change in FEV₁ between Visit 1 and Visit 3 in NERR subjects who received 21 days treatment (NERR-21) is at least 2.5% predicted greater than NERR subjects who received 14 days treatment (NERR-14) requires 570 subjects (285 per arm) who complete the study. STOP pilot data indicate a mean change (SD) in FEV₁ between Baseline and Day 28 in patients without an early response to be 4.0% predicted, 95% CI [1.9, 6.1]. Assuming two-sided alpha =0.05 and standard deviation =9.0% predicted, the NERR study has 91% power to detect a 2.5% greater increase in FEV₁ among those treated with 21 days compared to 14 day IV antibiotic. Because this trial will enroll a slightly different patient population (including home IV, excluding patients who receive <7 days of IV antibiotics), a blinded, interim assessment of change in FEV₁ % predicted and variance (pooled) will be performed and expected sample size may be adjusted for either the ERR or NERR groups.

Based on STOP pilot data, we anticipate 1:2 allocation of subjects into the ERR and NERR groups. To meet the enrollment goal of a minimum of 310 completed ERR subjects and a minimum of 570 completed NERR subjects), we will screen approximately 1330 subjects. Of these, we expect approximately 1236 subjects will be enrolled and randomized (assuming a conservative 7% drop-out rate between Visit 1 and Visit 2) and a minimum of 310 completed ERR subjects and a minimum of 570 completed NERR subjects (assuming an approximate 4% drop-out rate between Visit 2 and Visit 3).

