8 STUDY TREATMENTS

8.1 Method of Assigning Subjects to Response Group and Treatment Arms

All eligible subjects will undergo pulmonary function testing (spirometry) and complete a respiratory symptom score (CRISS) at Baseline (Visit 1) and at Day 7-10 (Visit 2). At Visit 2, subjects will be allocated to either the ERR or NERR group based upon their initial clinical response as determined by the change from Baseline in FEV₁ (percent of predicted as determined by GLI equations)^{18,19} and CRISS and then randomized to a treatment arm (duration nested within response group). The spirometry and CRISS measures must be present and entered into EDC for both Baseline (Visit 1) and Visit 2 for randomization to occur.

ERR subjects [$\geq 8\%$ predicted improvement in FEV₁ from Baseline (Visit 1) to Visit 2 and CRISS reduction of ≥ 11 points from Baseline (Visit 1) to Visit 2] will be randomized 1:1 to either 10 days (ERR-10) or 14 days (ERR-14) total IV antibiotic treatment duration while remaining subjects not meeting the ERR threshold will be randomized 1:1 to receive either 14 (NERR-14) or 21 (NERR-21) days total IV antibiotic treatment duration. A minimum of 310 subjects (155 per duration arm) will be allocated to the ERR group and a minimum of 570 subjects (285 per duration arm) to the NERR group. Randomization will occur by a predetermined scheme. Within each response group, subjects will be stratified by Visit 1 FEV₁ (FEV₁ < 50% of predicted versus $\geq 50\%$ predicted), number of IV-treated exacerbations in prior year (0-1 versus 2+ in prior year), location of IV treatment by Visit 2 (exclusively home versus any hospital nights), and use of systemic corticosteroids by Visit 2.

Randomization will occur centrally using a web based randomization system linked to the electronic data capture (EDC) system. Only authorized site personnel are given access to the EDC system. Authorized site personnel will enter subject eligibility information as well as any information needed for randomization stratification. The system will provide the appropriate authorized site personnel with a randomization assignment for that subject that matches a specific treatment duration.

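### Does the unexplained step from 310 and 570 completers to 1330 screened, with a per-protocol primary ERR analysis, leave the ERR comparison short of its stated power?

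*Protocol*

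**What the plan says.** Protocol 15.7 and the matching synopsis entry give the sizing. For ERR, the non-inferiority comparison "requires 310 subjects (155 per arm) who complete the study", with 93% power for a 3.5% predicted margin, SD 9.0, a true difference of zero and two-sided alpha 0.05. For NERR, 570 completers (285 per arm) give 91% power for a 2.5% predicted difference. The stated 95% CI half-widths are 2% and 1.5%.

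The recruitment text then reads: "Based on STOP pilot data, we anticipate 1:2 allocation of subjects into the ERR and NERR groups". The target is put as "a minimum of 310 completed ERR subjects and a minimum of 570 completed NERR subjects, we will screen approximately 1330 subjects". After a 7% loss before Visit 2, "we expect approximately 1236 subjects will be enrolled and randomized", and the completer minimums are given "assuming an approximate 4% drop-out rate between Visit 2 and Visit 3". The same section provides for a blinded look at FEV1 change and pooled variance, after which "expected sample size may be adjusted for either the ERR or NERR groups".

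Protocol 8.1 uses a different verb for the same number: "A minimum of 310 subjects (155 per duration arm) will be allocated to the ERR group".

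Protocol 15.1 and SAP 1.4 and 2.5 make the per-protocol (PP) population primary for ERR, with ITT as the repeat analysis. PP removes anyone with a Section 13 violation. Those violations include treatment duration outside the permitted tolerance, which the synopsis sets at one day either way for both ERR arms. Protocol 12.1 keeps such subjects on study.

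**The concern.** Two things look wrong on a first reading. First, the screening number does not follow from the inputs printed beside it: working back from 310 and 570 gives about 1042, not 1330. Power quoted for one set of counts next to recruitment planned for another suggests an arithmetic slip.

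Second, the 93% is tied to subjects who complete, but the ERR hypothesis is tested in the PP set. A subject who misses the assigned duration by more than the tolerance can complete Visit 3 and still be outside PP. In an open-label trial of treatment duration that is a foreseeable violation, and no exclusion rate or inflation is stated. If only 310 ERR subjects completed and some were then excluded, the primary non-inferiority test would have less than its stated power. The wording in 8.1 (allocated rather than completed) adds to the doubt about what the 310 counts.

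**Working it through.** **Inputs** (Protocol 15.7): 155 and 285 completers per arm; SD 9; margin 3.5; difference 2.5; ERR share one third; losses of 7% and 4%; 1330 screened; 1236 randomized. SAP 2.5 tests ERR at one-sided 0.025, the equivalent of the protocol's two-sided 0.05. The documents give no PP exclusion rate, so the rates below are assumptions, taken as equal in the two arms.

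**1. The plan's own figures reproduce.** Power = Φ(δ / (9·√(2/n)) − 1.96); half-width = 1.96·9·√(2/n).
- ERR, n = 155, δ = 3.5: 92.8%, half-width 2.00 (stated 93%, 2%).
- NERR, n = 285, δ = 2.5: 91.2%, half-width 1.48 (stated 91%, 1.5%).
- 1330 × 0.93 = 1236.9 (stated about 1236).

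**2. Backward from the minimums.** At 1:2 the ERR group is limiting: 310 × 3 = 930 completers; 930 / 0.96 = 969 randomized; 969 / 0.93 = 1042 screened. The stated 1330 is 288 (28%) higher.

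**3. Forward from 1330.** 1236 × 0.96 = 1186.6 completers; one third is 395.5 ERR and two thirds 791.0 NERR. These exceed the minimums by about 86 and 221. At those counts ERR power is 97.2% (n = 197.8 per arm, half-width 1.77) and NERR power 97.4% (n = 395.5 per arm, half-width 1.25).

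**4. Range of ERR share that still meets both minimums.** Lower end 310 / 1186.6 = 26.1%; upper end 1 − 570 / 1186.6 = 52.0%. The anticipated 33.3% lies well inside.

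**5. PP loss that the ERR group can absorb.** 1 − 310 / 395.5 = 21.6% of completers before the PP count reaches 310.

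| Assumed PP exclusion | ERR power from 396 completers | ERR power from 310 completers |
|---|---|---|
| 0% | 97.2% | 92.8% |
| 10% | 95.6% | 90.1% |
| 20% | 93.3% | 86.5% |
| 30% | 89.9% | 81.7% |

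The middle column is the one that follows from the stated recruitment. The right-hand column requires ERR to end at its minimum.

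**6. Both risks together.** At an assumed 30% ERR share there are 1186.6 × 0.30 = 356.0 ERR completers, and the PP allowance is 1 − 310 / 356.0 = 12.9%. With 20% excluded at that share, 284.8 remain and power is 90.7%. At a share of about 26% the allowance is nil.

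**The case for a change.** The strongest case for a change is that a reader cannot tell what the surplus is for, and that the same surplus has to cover two risks. The protocol itself says its population differs somewhat from the pilot's, so the 1:2 split is uncertain, and a lower ERR share uses up the room that PP exclusions would need. The blinded reassessment names FEV1 change and variance, not adherence. On this view a sentence naming the purpose of the surplus, and a PP basis for the 310, would cost almost nothing.

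Part of this stands. The purpose of the surplus is not stated, and 8.1 and 15.7 use different verbs for the 310. But the consequence is small. Even the combined case of a 30% share and 20% exclusion gives 90.7% power, and both of those inputs are assumed. The one-day tolerance narrows what counts as a duration violation. Missed Visit 3 spirometry is also a Section 13 violation, so part of the PP loss is already in the 4%. Adherence to assigned duration is monitored from the first 100 enrolled (Protocol 15.6) and at the 10% review (SAP 1.2). Protocol 15.6 places sample-size adaptation in a separate monitoring plan, and Section 14 refers interim details to a DMC Charter. Neither is among the documents reviewed, so it cannot be said that PP loss is ignored there.

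A rewrite would also have to supply what the documents lack: a PP exclusion rate with no source, and a reason for 1330 that only the sponsor knows. Adding a rule that power is restated rather than enrolment extended would turn an approximate number into a cap and sit badly with the provision that "expected sample size may be adjusted for either the ERR or NERR groups".

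**Conclusion.** No change follows. Power is quoted at a floor and recruitment is planned above it, which is coherent and conservative. Every stated power, half-width and randomization figure reproduces; the only unexplained item is a surplus of about 288 screened, and it works in the trial's favour. On the plan's own assumptions (1:2 split, 7% and 4% losses, SD 9, 1330 screened) the primary PP analysis of ERR has about 97% power with no exclusions, and keeps the stated 93% until about 22% of completers are excluded.

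The conclusion rests on recruitment running to about 1330 and on an ERR share near one third. It would weaken if ERR enrolment closed at 310 completers, which no section provides for, or if the share fell towards 26%. Inference in any case rests on the observed difference and its 95% CI (Protocol 15.3 and 15.7), so imprecision from a smaller PP set would show in the interval. The difference between allocated in 8.1 and completed in 15.7 is loose wording; an analyst would take the fuller statement in 15.7 as the target.

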16 DATA COLLECTION, RETENTION AND CLINICAL MONITORING

16.1 Data Collection Instruments

The Investigator will prepare and maintain adequate and accurate source documents designed to record all observations and other pertinent data for each subject who signs informed consent.

Study personnel at each site will enter data from source documents corresponding to a subject's visit into the protocol-specific electronic CRF when the information corresponding to that visit is available. Subjects will not be identified by name in the study database or on any study documents to be collected by the Sponsor (or designee), but will be identified by a site number, subject number and, for US sites only, initials.

If a correction is required for a CRF, the time and date stamp tracks the person entering or updating CRF data and creates an electronic audit trail.

The Investigator is responsible for all information collected on subjects enrolled in this study. All data collected during the course of this study must be reviewed and verified for completeness and accuracy by the Investigator. A CD containing the CRF data will be provided to the site to be retained with the essential documents at the Investigator's site at the completion of the study.

16.2 Data Management Procedures

TDNCC utilizes Medidata Solutions, Inc. (Medidata) Rave for their EDC studies. The Medidata Rave EDC system is designed to be US Code of Federal Regulations (CFR) 21 Part 11 compliant, with a robust audit trail system and electronic signature capabilities. Study personnel at each site will enter data from a subject's visit onto electronic CRF screens via a web browser. Study subjects will not be identified by name in the study database or on any data capture screens, but will be identified by initials and a unique subject identification number. Only study personnel at the individual sites will be able to link the study ID to the subject's name. The Biostatistics and Clinical Data Management group of the TDNCC will be responsible for data processing, in accordance with procedural documentation. Database lock will occur once quality assurance procedures have been completed. All procedures for the handling and analysis of data will be conducted using good computing practices for the handling and analysis of data for clinical trials.

16.3 Data Quality Control and Reporting

After data have been entered into the study database, data validation checks will be applied on a regular basis. Queries are entered, tracked, and resolved through the EDC system directly. The study database will be updated in accordance with the resolved queries. All changes to the study database will be documented in an audit trail.

16.4 Security and Archival of Data

The EDC system is hosted by Medidata; the data are stored at Medidata's primary data center in Houston, Texas, with fail-safe data centers in New Jersey. Data are regularly backed up by Medidata.

Medidata maintains 21 CFR Part 11-compliant electronic systems, with procedures in place to safeguard against unauthorized acquisition of data. Any authorized communication with the Medidata servers at the Houston Data Center is conducted via SSL (128-bit) encryption. Robust password procedures, consistent with 21 Part 11, are in place. Robust physical security procedures are in place at the Houston Data Center to prevent unauthorized personnel physical access to the server rooms. EDC account access is maintained and monitored by the Biostatistics and Clinical Data Management group of the TDNCC.

Other databases will be stored on Seattle Children's servers and are safeguarded against unauthorized access by established security procedures. Network accounts are password protected and maintained and monitored by the Seattle Children's Information Technology group. Data is backed up regularly according to the Information Services group's procedures.

Note that there is an intention to make biospecimens and associated data available to investigators for future exploration. The biospecimens will be collected under IRB/IEC approval, processed according to a rigorous standard operating procedure and stored at a central facility, with appropriate procedures to enable long term, stable storage. Researchers may apply, via a standardized process, for use of de-identified data and specimens for research purposes. Applications will undergo a scientific review process administered through CFFT. When applying for use of data or specimens, the applicant must agree to: (1) use the data and specimens only for research purposes and to not make any attempts to try to identify any individual subject; (2) securing the data and specimens using appropriate methods; and (3) destroy or return the data (and specimens) in accordance with the specimen/data use agreement after analyses are completed. Before data or specimens will be released to an investigator, documentation of IRB/IEC exemption or approval from their institution must be provided to the CFFT.

16.5 Availability and Retention of Investigational Records

The Investigator must make study data accessible to the monitor, other authorized representatives of the Sponsor (or designee), IRB/IEC, and Regulatory Agency (e.g., FDA) inspectors upon request. A file for each subject must be maintained that includes the signed Informed Consent, HIPAA Authorization and Assent Form and copies of all source documentation related to that subject. The Investigator must ensure the reliability and availability of source documents from which the information on the CRF was derived.

All study documents (e.g., patient files, signed informed consent forms, copies of CRFs, Essential Document and Study Reference Binders) must be kept secured for a period of one year

after database lock and accessible for 5 years following database lock. There may be other circumstances for which the Sponsor is required to maintain study records and, therefore, the Sponsor should be contacted prior to removing study records for any reason.

